2.1 Content of Clinical Studies

2.1.1 Evaluation of the Diagnostic Performance of 18F-FAPI PET/CT

This study aims to evaluate the sensitivity, specificity, and accuracy of 18F-FAPI PET/CT in lung cancer patients, providing a basis for clinical application. By performing 18F-FAPI PET/CT scans on lung cancer patients and collecting relevant data, the performance of this modality in early diagnosis, staging, and recurrence monitoring was analyzed. The goal is to provide a scientific basis for clinical decision-making in the diagnosis and treatment of lung cancer.

2.1.2 Comparative Study of 18F-FAPI PET/CT with Other Imaging Techniques (CT, MR, FDG PET/CT)

A comparative study of 18F-FAPI PET/CT versus conventional imaging modalities (CT or MR) or 18F-FDG PET/CT in lung cancer patients, evaluating the differences in tumor detection sensitivity, specificity, and accuracy among various imaging techniques. The study aims to clarify their advantages in clinical applications for lung cancer. The research will focus on analyzing the differences in tumor size, location, metastasis, and pathological characteristics among the imaging techniques, exploring the potential of 18F-FAPI PET/CT in improving diagnostic accuracy and early detection of lung cancer.

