2.1.4 Evaluation of 18F-FAPI PET/CT in Predicting Lung Cancer Prognosis

Based on TNM staging and PERCIST criteria, this study evaluates the post-treatment reassessment, efficacy prediction, and prognostic assessment (AUC comparison of PFS/OS) of 18F-FAPI PET/CT in lung cancer. The research will analyze the monitoring capability of 18F-FAPI PET/CT in assessing tumor response post-treatment

and its value in prognostic evaluation, aiming to provide clinicians with a more precise tool for assessing treatment efficacy. It tracks the time from diagnosis to specific events (e.g., CR, PR, SD, PD, recurrence, death) in lung cancer patients to identify influencing factors. Survival rates over time are plotted using Kaplan-Meier curves to visually compare survival differences across groups. Additionally, Cox proportional hazards model multivariate regression quantifies the contribution of factors such as age and pathological stage to survival risk, aiding clinical decision-making.

3 Mechanism of Action and Research Scope of 18F-FAPI PET/CT

18F (97% β^+ , $T_{1/2}=109.7$ minutes) is currently the most widely used radionuclide in PET/CT due to its chemical, physical, and nuclear properties, making it an ideal choice for peptide-based imaging. 18F-FDG is the most commonly used PET tracer in oncology, serving as the preferred modality for tumor diagnosis and therapeutic efficacy evaluation. However, 18F-FDG PET/CT exhibits relatively low sensitivity and specificity for tumors with low invasiveness, high differentiation, or mucinous tissue, while physiological uptake in organs such as the oropharynx and digestive tract often obscures tumor metabolism and uptake. Additionally, mediastinal and hilar lymph nodes still show a high rate of false positives on 18F-FDG PET, whereas 18F-FAPI PET/CT improves the specificity of lymph node diagnosis. Furthermore, compared to 68Ga-labeled tracers, 18F-labeled FAPI has better resolution potential due to its lower positron energy. Therefore, 18F-labeled FAPI holds significant clinical value and promising prospects.

4 Indications, Contraindications, and Precautions

4.1 Eligibility Criteria: Patients with suspected or confirmed lung cancer who have undergone 18F-FAPI PET/CT

4.2 Exclusion Criteria:

- (1) Concurrent presence of other active malignant tumors or a history of other malignant tumors within the past 5 years;
- (2) Severe uncontrollable diseases or active infections;
- (3) Ineligible participants for informed consent.

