5.1 Research Methods

This study adopted a prospective, multicenter research design. It aimed to evaluate the diagnostic research and exploration of 18F-FAPI PET/CT in lung cancer patients. A total of 120 subjects were planned to be enrolled from three centers nationwide (The First Affiliated Hospital of Zhejiang University School of Medicine, Zhejiang Provincial People's Hospital, and Shulan Hangzhou Hospital).

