5.3 Subject Selection

5.3.1 Eligibility Criteria for Subjects

- (1) Patients with suspected or confirmed lung cancer
- (2) 18F-FAPI PET/CT has been performed.

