5.3.3 Subject Loss to Follow-up

Lost to follow-up: Participants did not complete the specified follow-up period but did not 'formally' withdraw from the clinical trial.

If a participant fails to respond to three telephone follow-ups, a registered mail letter must subsequently be sent to the participant. If the participant does not respond to the letter, the participant will be considered as having "lost to follow-up" for current study visits or telephone contacts. The investigator must record this information on the original data sheet. The investigator must report this information to the relevant ethics committee in accordance with the procedures of their institution.

For cases with lost-to-follow-up, the reasons should be explained, and their e-CRF forms should be retained for review. No diagnostic efficacy statistical analysis will be performed, but the patients who undergo examinations may participate in safety analysis as appropriate.

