6.2 Subject Screening

Participants will sign an informed consent form prior to enrollment in this study. Investigators will explain the nature, purpose, and risks of the study and provide the participants with an informed consent form. Participants will be given sufficient time to consider the significance of the study before deciding whether to participate. Any modifications to the informed consent form must be notified and approved by the ethics committee prior to participant enrollment.

First, participants must undergo an informed consent process and sign an informed consent form. Subsequently, eligible subjects are screened from the target population according to the pre-established inclusion and exclusion criteria of this study, after which they may be considered for inclusion in the research.

Baseline data collection included general examinations, medical history, and laboratory tests conducted at the same hospital or external hospitals within one week prior to the signing of the informed consent form. Adverse events and concomitant medications were collected after the signing of the informed consent form.

history-taking

Conduct a detailed inquiry into the patient's medical history to clarify symptoms, signs, and prior medical history (e.g., tumor history, surgical history, biopsy history, radiotherapy history, chemotherapy history, family history,

allergy history, etc.), relevant laboratory tests, previous imaging findings (including plain radiography, ultrasound, CT, MRI, as well as 18F-FDG PET/CT, PET/MR, etc.), and recent pathological results (including tumor grading and Ki-67 index, etc.), along with the patient's follow-up medical records.

Image judgment criteria

The uptake of imaging agents in tissues or organs that normally do not take up such agents can be considered pathological. Typically, 18F-FAPI is rapidly cleared from the bloodstream. Taking 18F-FAPI as an example, radioactive distribution can be observed in the salivary glands, thyroid, liver, biliary tract, gallbladder, pancreas, adrenal glands, kidneys, intestines, collecting system, and bladder, with almost complete excretion through the biliary tract. There is minimal distribution of the radioactive imaging agent in brain tissue. Compared to the liver, if the uptake is significantly increased in a lesion, it is considered positive, suggesting malignant tumors. Generally, moderate intestinal distribution and non-focal intestinal uptake are considered non-pathological.

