10.1 Definition of Adverse Events

Adverse medical events (AMEs) in clinical trials during follow-up, including discomfort symptoms, signs or abnormal laboratory findings, and imaging abnormalities.

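### The inclusion criteria require a completed 18F-FAPI scan, adverse events are collected only after consent, and the protocol never says which comes first

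*Protocol*

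**What the plan says.** The entry criteria appear in three places, and each asks for a scan that already exists. Section 4.1 describes the population as "Patients with suspected or confirmed lung cancer who have undergone 18F-FAPI PET/CT". Section 5.3.1 lists as a separate item that "18F-FAPI PET/CT has been performed", and the synopsis repeats that item. Eligibility is verified through the electronic medical record (section 5.3.3 on withdrawal). Patients treated at the hospital need no study visit (visit plan in the synopsis), and section 5.2.1 states that there is no blinding.

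Other sections read as if the scan belongs to the study and follows consent:

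- Section 5.1: "This study adopted a prospective, multicenter research design".
- Section 2.1.1: "By performing 18F-FAPI PET/CT scans on lung cancer patients and collecting relevant data".
- Section 6.1 lets the study begin only once the consent form is signed.
- Section 6.2: "First, participants must undergo an informed consent process and sign an informed consent form"; screening against the criteria comes next.

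On safety, section 6.2 says "Adverse events and concomitant medications were collected after the signing of the informed consent form", and section 10.1 defines the events as "Adverse medical events (AMEs) in clinical trials during follow-up". Section 5.3.3 on loss to follow-up adds that "the patients who undergo examinations may participate in safety analysis as appropriate".

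No section places the scan before or after consent.

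**The concern.** In a diagnostic accuracy study, the order of enrolment and index test is a core design feature, and these sections do not agree on it. Two things depend on it.

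The first is the primary endpoint: sensitivity, specificity and accuracy. If patients become eligible only once scanned, are identified from the record, and nobody is blinded, then whoever approaches them can have the index result to hand. The protocol does not ask for consecutive enrolment, so nothing in it prevents the result from influencing who is approached. A larger sample does not remove bias of that kind.

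The second is safety. If the scan precedes consent, an immediate reaction to the tracer occurs before collection opens, although a safety analysis of examined patients is foreseen.

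There is also a practical risk. One of the three centres could follow the text by enrolling only patients already scanned, and another by consenting first and scanning afterwards. The pooled data would then mix two designs.

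**Working it through.** **Step 1. Which orders does the text allow?**

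| Order | Fits the criterion as worded? | Index result available at consent? | Acute reactions collected? |
|---|---|---|---|
| Scan, consent, screening | Yes | Yes | No |
| Consent, scan, screening | Yes | No | Yes |
| Consent, screening, scan | No: at screening the scan has not been done | No | Yes |

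The first two orders comply with the text. The third, the usual one for a prospective diagnostic study, is the only one that the criterion excludes when read literally. Record-based verification and the absence of study visits fit the first order. The scan wording of 2.1.1 and the consent rule of 6.1 fit the second better.

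**Step 2. What could selection on the result do?** The protocol gives no figure for this, so the following is an illustration.

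Inputs: sensitivity (Se) 0.92 and specificity (Sp) 0.96, the planning values in section 7.1. Assumption: scan-negative patients are enrolled at r times the rate of scan-positive patients, with the same r in patients with and without cancer. The value r = 1 means no selection.

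Among patients with cancer, a fraction Se is scan-positive (enrolled at relative rate 1) and 1 − Se is scan-negative (rate r). Among patients without cancer, Sp is scan-negative (rate r) and 1 − Sp is scan-positive (rate 1). Hence:

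- apparent Se = Se / (Se + (1 − Se)·r)
- apparent Sp = Sp·r / (Sp·r + (1 − Sp))

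| r | Apparent Se | Apparent Sp |
|---|---|---|
| 1.0 | 0.920 | 0.960 |
| 0.9 | 0.92/0.992 = 0.927 | 0.864/0.904 = 0.956 |
| 0.7 | 0.92/0.976 = 0.943 | 0.672/0.712 = 0.944 |
| 0.5 | 0.92/0.960 = 0.958 | 0.480/0.520 = 0.923 |

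At r = 0.5 the shifts are +0.038 and −0.037. Both are smaller than the allowable error of 0.08 stated in section 7.1.

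The shift grows when true accuracy is lower. With Se = Sp = 0.85 (also an assumption), r = 0.5 gives Se 0.85/0.925 = 0.919 and Sp 0.425/0.575 = 0.739. The shifts are +0.069 and −0.111, and the second exceeds 0.08.

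**Step 3. What would the safety data miss?** Under scan-first, the gap runs from injection to signature. Events arising after signature are collected under 6.2. Section 2.1.4 foresees reassessment with 18F-FAPI PET/CT after treatment, and those scans would fall after consent. The gap is therefore limited to acute reactions to the scan on which entry is based.

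**The case against.** The strongest reply is that the past tense proves little. The protocol uses it for work not yet done, including subgroup analysis (2.1.3), statistical analysis (7.3) and adverse-event collection itself (6.2). The criterion may only mean that an unscanned patient cannot be analysed. Sections 6.1 and 6.2 put consent first, and section 18 requires investigators to be trained beforehand in injection and scanning, which suggests scans done within the study. Excluding pregnant and lactating women also fits a check made before injection more naturally. All of this stands: consent followed by the scan is not ruled out, and under that order the adverse-event window covers the injection.

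A reader might infer more than the text supports, in four ways:

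- *That patients will be enrolled with the result known and selected on it.* The result would be available under scan-first, but no section says that recruiters read it or act on it, and no criterion refers to a positive or negative scan.
- *That safety data for the tracer would be empty.* Delayed events and later scans would still be captured. Safety is neither a primary nor a secondary endpoint, and the safety analysis is mentioned only in passing, for patients lost to follow-up.
- *That the prospective label is false.* Enrolling after the scan and then following pathology and survival is still prospective for those outcomes.
- *That the figures above measure a bias in this trial.* The enrolment ratios have no source in the protocol.

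What the reply does not remove is the conflict itself. All three statements of the criterion require a completed scan, and no sentence elsewhere settles the order.

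**Conclusion.** The point holds as an unresolved contradiction about the order of scan, consent and adverse-event collection. As worded, the protocol permits enrolment from the record with an unblinded index result available, and it permits acute tracer reactions to fall before collection starts. It does not establish that either will happen.

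The possible size is moderate at the protocol's own planning values: with relative enrolment of scan-negatives between 1.0 and 0.5, sensitivity would appear as 0.92 to 0.958 and specificity as 0.96 to 0.923. This rests on an assumed ratio that is equal in patients with and without cancer. Without selection on the result there is no shift. The change is worth making because the primary endpoint is exposed and the correction is cheap.

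**What to change.** Reconcile the sections as follows:

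1. In the synopsis, 4.1 and 5.3.1, reword the criterion to *scheduled to undergo 18F-FAPI PET/CT*.
2. State in 6.2 that consent and confirmation of eligibility precede tracer injection.
3. Require that eligible patients be approached consecutively at each centre.
4. Start adverse-event collection at injection, and align 6.2 and 10.1 with that.

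If already-scanned patients must remain eligible, enrol them consecutively regardless of scan result, report them separately, and leave them out of the denominator for acute events.

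Cost: a protocol amendment and a consent step at scan booking in three centres. No extra scans or patients are needed. Patients scanned before consent would no longer count under the main option, so recruitment may be slightly slower. If consent before the scan was always intended, the change is little more than wording.

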5.1 Research Methods

This study adopted a prospective, multicenter research design. It aimed to evaluate the diagnostic research and exploration of 18F-FAPI PET/CT in lung cancer patients. A total of 120 subjects were planned to be enrolled from three centers nationwide (The First Affiliated Hospital of Zhejiang University School of Medicine, Zhejiang Provincial People's Hospital, and Shulan Hangzhou Hospital).

5.2 Measures to Reduce or Avoid Bias

5.2.1 Blinding

No blinding.

5.2.2 Clinical Indicator Assessment

The gold standard is the pathological result of biopsy or surgery.

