Visit Plan	For patients under treatment and follow-up at this hospital, no in-person visits are required; relevant data can be obtained from the electronic medical record (EMR) system and imaging system of this hospital. For patients not receiving treatment at this hospital, a telephone follow-up protocol is implemented to obtain relevant pathological results.

research report	The study plans to enroll 120 eligible patients within 3 years, followed up their pathological results, and conduct statistical analysis.
statistical analysis	Statistical analysis was performed using SPSS 17.0. The diagnostic sensitivity, specificity, and negative/positive predictive values were calculated using a four-cell table. The area under the ROC curve and the optimal cutoff value (SUV optimal cutoff) were evaluated by ROC curve analysis. The consistency between 18F-FAPI PET diagnosis and pathological diagnosis was assessed using the kappa test. A p-value <0.05 was defined as statistically significant.

English abbreviation reference

PET	Positron emission tomography
CT	Computed tomography
ROC	Receiver operating characteristic curve
FAPI	Fibroblast activation protein inhibitor

1 Research Background

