5.4 Study Endpoints

Primary endpoint: Diagnostic efficacy of 18F-FAPI PET/CT in lung cancer patients (sensitivity, specificity, accuracy)

secondary end points:

- ① Compare the diagnostic performance differences of 18F-FAPI PET/CT with CT, MR, and 18F-FDG PET imaging in clinical applications for lung cancer;
- ② Analysis of diagnostic differences in the subgroup of patients (pathological, genetic, etc.) using 18F-FAPI PET/CT;
- ③ Evaluation of 18F-FAPI PET/CT in predicting lung cancer prognosis.

6 Research Procedures and Operational Standards

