7.3 Statistical Methods

Statistical analysis was performed using SPSS 17.0. The diagnostic sensitivity, specificity, and negative/positive predictive values were calculated using a four-cell table. The area under the ROC curve and the optimal cutoff value (SUV optimal cutoff) were evaluated by ROC curve analysis. The consistency between 18F-FAPI PET/CT diagnosis and pathological diagnosis was assessed using the kappa test. A p-value <0.05 was defined as statistically significant.

Statistical analysis was performed using SPSS 17.0.

① Diagnostic performance evaluation, four-grid table index calculation:

Sensitivity = True positives / (True positives + False negatives) × 100%

Specificity = True Negative / (True Negative + False Positive) × 100%

Positive predictive value = true positive / (true positive + false positive)

Negative predictive value = true negative / (true negative + false negative)

② ROC curve analysis:

Calculate the area under the curve (AUC) and evaluate diagnostic performance (AUC>0.9 indicates excellent, 0.8-0.9 indicates good, 0.7-0.8 indicates moderate).

Determine the optimal cutoff for SUV using the maximum Youden index.

③ consistency check

The consistency between 18F-FAPI PET/CT and pathological diagnosis was evaluated using the Kappa coefficient.

Kappa>0.8: Excellent consistency;

0.6-0.8: High consistency;

<0.6: Consistency should be interpreted with caution.

Bilateral test, $p<0.05$ defined as significant difference.

④ survival analysis

Kaplan-Meier method:

Collect baseline PET parameters (lesion SUVmax, lesion SUVmean, MTV, LTV, bone marrow SUVmax, etc.), and plot PFS/OS curves according to treatment response (CR/PR vs. SD/PD), pathological response (e.g., MPR status), or PET parameter grouping (e.g., high/low SUVmax). Compare the significance of survival differences between groups using the Log-rank test ($p<0.05$).

Cox proportional hazards model:

Univariate analysis: Screening of clinical variables associated with PFS/OS (age, stage, SUVmax, MTV, etc.).

Multivariate analysis: Significant univariate variables ($p<0.1$) were included, with quantified hazard ratios (HR) and 95% confidence intervals.

Verify the proportional hazards assumption (Schoenfeld residual test).

8 Data Recording and Management

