8.1 Investigator Data Records

- 1) For all eligible participants who have signed the informed consent form, their relevant data and laboratory test results must be meticulously and thoroughly documented.
- 2) All imaging data were interpreted by two attending physicians with over 5 years of experience in nuclear medicine, and the chief physician provided the final consensus interpretation for any questionable cases.
- 3) Original data records, signed by the investigator and dated.

4) Confirm that all adverse events have been documented, and that serious adverse events have been reported and recorded in accordance with relevant procedures in a timely manner.

9 Expected Research Progress

Study recruitment period: 36 months

Observational study duration: This study was an observational study, with patient mortality serving as the endpoint of follow-up.

10 Adverse Event Assessment and Reporting

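### Tissue is the only reference standard but is not required of suspected patients, so specificity above all, and sensitivity to a lesser degree, are open to verification bias

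*Protocol*

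**What the plan says.** Four parts of the protocol bear on this.

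- **Reference standard (5.2.2).** "The gold standard is the pathological result of biopsy or surgery". No second reference, such as clinical or imaging follow-up, is given for patients without tissue.
- **Population (5.3.1).** The two inclusion criteria are "Patients with suspected or confirmed lung cancer" and "18F-FAPI PET/CT has been performed". Neither these nor the exclusions in 5.3.2 require that tissue exists or is planned.
- **Follow-up.** In the summary's Visit Plan, for patients treated elsewhere, "a telephone follow-up protocol is implemented to obtain relevant pathological results". For patients of the hospital, unspecified relevant data come from its records. The summary's research report row again names only pathological results. Section 9 adds: "This study was an observational study, with patient mortality serving as the endpoint of follow-up". That longer follow-up feeds the survival analyses in 2.1.4 and 7.3, not the diagnostic reference.
- **Analysis (5.4 and 7.3).** The primary endpoint is sensitivity, specificity and accuracy. "The diagnostic sensitivity, specificity, and negative/positive predictive values were calculated using a four-cell table". No adjustment for incomplete verification is described.

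Section 5.2.1 says that there is no blinding. The image criteria in 6.2 say of uptake relative to liver: "if the uptake is significantly increased in a lesion, it is considered positive, suggesting malignant tumors". The paragraph on loss to follow-up (the second section numbered 5.3.3) removes lost patients from the diagnostic analysis. It does not address a patient who is fully followed but never sampled.

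**The concern.** A patient needs both a scan result and a reference result to enter a four-cell table. Here the reference result exists only if someone decided to take tissue, and nothing in the protocol keeps that decision independent of the scan. A scan read as suggesting malignancy may prompt a biopsy or an operation; a negative scan in a suspected patient may lead to watching.

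If that happens, the patients missing from the table are mostly scan-negative, that is, the false negatives and true negatives. Losing false negatives raises observed sensitivity, and losing true negatives lowers observed specificity. Specificity is the more exposed, because only suspected patients can turn out not to have lung cancer. All of the information on specificity comes from the group in which tissue is not assured.

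This cannot be left to an analysis plan. The protocol itself fixes the reference, the population and what is collected, and no later analysis can recover a disease status that was never recorded.

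**Working it through.** **Inputs.** Sensitivity Se = 0.92 and specificity Sp = 0.96 are the protocol's planning values (7.1). The protocol gives no rate at which patients obtain tissue. Let v+ and v− be the shares of scan-positive and scan-negative patients with tissue, and r = v+/v−. All values of v+, v− and r below are assumptions.

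**Formulas**, if tissue depends only on the scan result:

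- Observed Se = r·Se / (r·Se + (1 − Se))
- Observed Sp = Sp / (Sp + r·(1 − Sp))

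**Step 1: all patients suspected.**

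| r | Observed Se | Observed Sp |
|---|---|---|
| 1 | 0.92/1.00 = 0.920 | 0.96/1.00 = 0.960 |
| 2 | 1.84/1.92 = 0.958 | 0.96/1.04 = 0.923 |
| 4 | 3.68/3.76 = 0.979 | 0.96/1.12 = 0.857 |

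The row r = 1 returns the protocol's own values, so equal verification gives no bias. At r = 2 sensitivity is 0.038 too high and specificity 0.037 too low. At r = 4 the shifts are 0.059 and 0.103.

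The same calculation with v+ = 0.95:

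| v− | Observed Se | Observed Sp |
|---|---|---|
| 0.7 | 0.940 | 0.946 |
| 0.5 | 0.956 | 0.927 |
| 0.3 | 0.973 | 0.883 |

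**Step 2: part of the cohort already confirmed.** Let c be the share confirmed and fully verified. Among suspected patients assume 60% prevalence, v+ = 0.95 and v− = 0.5. As shares of the cohort:

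- TP = c·0.92 + (1 − c)·0.6·0.92·0.95
- FN = c·0.08 + (1 − c)·0.6·0.08·0.5
- TN = (1 − c)·0.4·0.96·0.5
- FP = (1 − c)·0.4·0.04·0.95

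| c | Observed Se | Observed Sp | Expected TN + FP, of 120 enrolled |
|---|---|---|---|
| 0 | 0.5244/0.5484 = 0.956 | 0.927 | 23.0 + 1.8 |
| 0.3 | 0.64308/0.68388 = 0.940 | 0.927 | 16.1 + 1.3 |
| 0.7 | 0.80132/0.86452 = 0.927 | 0.927 | 6.9 + 0.5 |

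The sensitivity bias falls from 3.6 points to 2.0 and then 0.7. The specificity bias stays at 3.3 points: the factor (1 − c) cancels from TN/(TN + FP), because confirmed patients add nobody without disease.

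**Step 3: the other table measures.** With v+ = 0.95, v− = 0.5 and nobody confirmed, accuracy moves from 0.940 to 0.946 at 50% prevalence and from 0.932 to 0.950 at 70%. Among suspected patients the predictive values do not move under this model: v+ multiplies both TP and FP, and v− both TN and FN, so each cancels.

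**The case against.** The strongest reply is that the bias is conditional and the protocol does not show that the condition holds. Nowhere does it say that FAPI directs biopsy. Patients may also have CT, MR or FDG PET, and a FAPI-negative lesion that looks suspicious on one of those can still go to tissue. Unblinded reading does not by itself decide who is sampled; what matters is whether treating clinicians know the scan result. The summary can also be read as expecting pathology for all 120 patients. This stands as a limit on certainty. It does not remove the gap, because no criterion makes tissue a condition of entry and no rule covers patients without it.

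A second reply is that confirmed patients enter the table whatever the scan shows. That stands for sensitivity, as step 2 shows, but it does nothing for specificity.

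Two stronger readings are tempting and are not supported:

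- **That unsampled patients are certainly excluded and sensitivity is certainly inflated.** The protocol does not state the exclusion. It follows only because they have no reference result and no other rule exists. The inflation also needs unequal tissue rates.
- **That the sensitivity bias exceeds the allowable error of 0.08 stated in 7.1.** That needs a true sensitivity well below the planning value, such as 0.80, which the protocol does not give. At 0.92 the shifts are 0.038 (r = 2) and 0.059 (r = 4), both below 0.08. Only specificity at r = 4 passes it, with a shift of 0.103, and that margin was set for estimating sensitivity.

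Finally, pathology alone is a strict and recognised reference, and follow-up is a weaker one. That is a reason to report both, not to leave disease status uncollected.

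**Conclusion.** The point holds as a conditional risk to the primary endpoint. Sections 5.2.2, 5.3.1 and 7.3 together leave a followed but unsampled patient with no cell in the table. If scan-negative suspected patients get tissue less often than scan-positive ones, specificity is understated and sensitivity overstated.

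At the protocol's planning values, ratios from 1 to 4 give observed specificity from 0.960 down to 0.857, and observed sensitivity from 0.920 up to 0.979 when nobody is confirmed in advance. Confirmed patients can shrink the sensitivity bias to a point or two, so specificity is the main concern. The direction rests on unequal tissue rates. The size rests on the assumed ratio, the share already confirmed and, for the diluted figures, the 60% prevalence among suspected patients. None of these is in the protocol. The data-collection rule should be settled before more patients pass through follow-up.

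**What to change.** In 5.2.2, keep pathology as the reference wherever it exists. For enrolled patients without tissue, collect final diagnosis and lesion status over a fixed period stated in advance, using existing records, routine imaging reports and the telephone contact already planned. Then classify:

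- lung cancer, if it is later diagnosed;
- no lung cancer, only if records or routine imaging document resolution, stability or a benign diagnosis;
- unverified, in every other case.

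Amend the Visit Plan so that follow-up asks for this status as well as pathology. In 7.3, report the four-cell results with this composite reference and with pathology only, side by side, and give the number unverified by scan result.

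The cost is protocol wording, added case report form fields and the work of obtaining outside reports. A telephone answer alone cannot establish that a lesion is stable, so patients without routine imaging will often remain unverified. No additional scan or biopsy is asked for. The main downside is a less certain reference: a slow-growing cancer that looks stable would be counted as a true negative, which favours the scan. This is why the pathology-only table stays beside the composite. The last patients' status will also be known later than under the present plan.
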